# 7.1.2 Hypothesis

The hypotheses to be evaluated in the analysis of the primary efficacy endpoint are:

 $H_0$ :  $S(t)_{cabozantinb} = S(t)_{placebo}$ 

 $H_A$ :  $S(t)_{cabozantinb} \neq S(t)_{placebo}$ 

where  $S(t)_{Cabozantinib}$  and  $S(t)_{Placebo}$  are the survivor functions for the cabozantinib and placebo arms, respectively.

## 7.1.3 Primary Analysis

The primary analysis of OS will include all subjects in the ITT population.

The hypothesis testing between the two treatment arms will be performed using the stratified log-rank test with a 2-sided  $\alpha$ =0.05 level of significance. The stratification factors are as described in Section 2.5 and the values used for analysis will be those recorded in the (IxRS).

The median duration of OS and the associated 95% confidence interval (CI) for each treatment arm will be estimated using the Kaplan-Meier method. The stratified hazard ratio (HR) and its 95% CI will be estimated using a Cox proportional-hazard model with treatment group as the independent variable and stratified by the same randomization stratification factors as were used for the log-rank test.

The analysis of OS is event-based. Up to three analyses of OS are planned: two interim analyses and a final analysis that will occur when 311, 466 and 621 deaths (i.e. 50%, 75% and 100% deaths) have been observed respectively. Inflation of Type I error associated with interim analyses will be controlled using a Lan-DeMets O'Brien-Fleming alpha-spending function. The critical p-values (and observed HR) for rejecting the null hypothesis will be  $0.0031~(HR \le 0.70)$ ,  $0.0183~(HR \le .80)$  and  $0.044~(HR \le .84)$  at the time when 311, 466 and 621 deaths (50%, 75% and 100% information) are observed respectively. The actual critical values will depend upon the true number of events observed at each analysis. The interim analyses of OS are also described in section 7.4.

At an analysis time point, if the p-value for the stratified log-rank test is less than the critical value for rejecting the null hypothesis and the HR is < 1, the null hypothesis will be rejected

and it will be inferred that OS is superior in the cabozantinib arm compared to the placebo arm.

# 7.1.4 Exploratory Analyses

Overall survival analyses as described in section 7.1.3 will be conducted by censoring for subjects who receive a systemic NPACT or a local liver directed therapy after randomization.

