# 2.4 Power and Sample Size Justification

For the primary OS endpoint, up to three event-driven analyses are planned at 50%, 75%, and 100% information fraction (311, 466, and 621 deaths, respectively). A sample size of 760 subjects with a total of 621 events (and two interim analyses) provides the study with 90% power for a 2-sided log-rank test at 5% level of significance to detect a 31.6% increase in OS (HR = 0.76). Assuming a median OS of 8.2 months in the placebo arm (based upon the BRISK trial; Llovet 2012) and exponential distribution, this corresponds to median OS of 10.8 months in the cabozantinib arm.

In the current design, the minimum observed effect that would result in statistical significance for OS at the two interim and final analyses are 42.1% improvement (HR = 0.70, from 8.2 to 11.7 months), 25.7% improvement (HR = 0.80, from 8.2 to 10.3 months) and 18.4% improvement (HR = 0.84, from 8.2 to 9.7 months), respectively.

With an average accrual rate of 31.5 subjects per month and using a 2:1 treatment allocation ratio, an approximate total of 760 subjects (507 subjects in cabozantinib arm and 253 subjects in placebo arm) are required to observe the minimum number of events within the planned study duration (25 months accrual and approximately 38 months to observe the required events for OS). Currently since the average accrual rate is less than 31.5 subjects per month this will also prolong the study duration and time required to observe the required events for OS.

Power and sample size estimates were calculated using EAST v5 by Cytel Software.

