### 7.2.1.4 Sensitivity Analyses

The primary analysis (PFS1) and 2 types of sensitivity analyses (PFS2 and PFS3) are outlined in Table 3. These analyses will include all subjects in the ITT population. Summaries and graphs as described in section 7.1.3 will be presented.

The sensitivity analyses (PFS2 and PFS3) define additional clinical outcomes as events and also evaluate the impact of informative censoring.

For PFS2 analysis, the following are considered as events:

- Radiographic progression per RECIST 1.1
- Death due to any reason
- Treatment discontinuation due to clinical deterioration
- Receipt of systemic non-protocol anti-cancer therapy (NPACT)
- Receipt of local liver-directed NPACT
- Radiation (other than to bone)
- Surgery to resect tumor lesions

For PFS3 analysis, the following are considered as events:

- Radiographic progression per RECIST 1.1
- Death due to any reason
- Treatment discontinuation due to clinical deterioration

Table 3: Event and censoring rules for primary and sensitivity analyses of PFS

Count as censored						
or event at earliest						
outcome criterion		DEG4		DEG.		DEG.
met	PFS1		PFS2		PFS3	
Purpose	Primary		Sensitivity			nsitivity
Situation	Outcome	Date	Outcome	Date	Outcome	Date
No post baseline	Censored	Date of	Censored	Date of	Censored	Date of
assessment		randomization		randomization		randomization
Radiographic PD	Event	Date of PD	Event	Date of PD	Event	Date of PD
Death	Event	Date of death	Event	Date of death	Event	Date of death
Subsequent	Censored	Date of last	Event	Date of NPACT	Censored	Date of last
systemic or local		ATA on or				ATA on or
liver directed non-		prior to				prior to
protocol anti-		NPACT				NPACT
cancer therapy						
(NPACT)						
Radiation (other	Censored	Date of last	Event	Date of	Censored	Date of last
than to bone)		ATA on or		radiation		ATA on or
		prior to				prior to
		Radiation				Radiation
Surgery to resect	Censored	Date of last	Event	Date of surgery	Censored	Date of last
tumor lesions		ATA on or				ATA on or
		prior surgery				prior surgery
Event after more	Censored	Date of last	Censored	Date of last	Censored	Date of last
than two missed		ATA prior to		ATA prior to the		ATA prior to
ATAs (>126 days)		the missing		missing visits		the missing
		visits				visits
Treatment	NA	NA	Event	Date of	Event	Date of
Discontinuation				determination		determination
due to Clinical						
deterioration						
No Event by last	Censored	Date of last	Censored	Date of last	Censored	Date of last

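### The exploratory OS analysis in SAP 7.1.4 censors plainly at later anticancer therapy; if use of that therapy depends on prognosis and differs by arm, its hazard ratio is biased in a direction that cannot be known in advance

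*SAP*

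**What the plan says.** SAP 7.1.1 defines OS as time from randomization to death from any cause. Subjects still alive are censored at data cutoff, loss to follow-up or withdrawal of consent, so deaths after later anticancer therapy count. SAP 7.1.2 states the null as equality of two functions that "are the survivor functions for the cabozantinib and placebo arms, respectively". SAP 7.1.3 tests it in the ITT population with a stratified log-rank test and estimates the hazard ratio (HR) from a stratified Cox model.

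SAP 7.1.4 is one sentence. The 7.1.3 analyses "will be conducted by censoring for subjects who receive a systemic NPACT or a local liver directed therapy after randomization". NPACT is non-protocol anticancer therapy. No date for the censoring is given; the start of the therapy is the natural reading.

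The other exploratory OS work (covariate Cox models and subgroups in protocol 9.2.3, subgroups in SAP 7.6) leaves the event and censoring rules alone. SAP 7.3 places everything beyond the OS, PFS and ORR tests outside Type I error control. For PFS, SAP 7.2.1.4 has two sensitivity analyses that "define additional clinical outcomes as events and also evaluate the impact of informative censoring".

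**The concern.** Censoring a subject at the start of NPACT treats that subject's later risk of death as the same as that of subjects in the same arm and stratum who have not started it. Protocol 3.6.1 and SAP 2.1 make the need for systemic or liver-directed therapy a reason to end study treatment, so its start is tied to the course of disease. Fitness to receive another treatment is also likely to matter.

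If prognosis drives NPACT and the arms use it at different rates, the two risk sets drift apart in prognosis and the HR reflects that drift. A reader would naturally turn to 7.1.4 to ask whether later therapy diluted or explained the OS result. The answer could then look like confirmation, enlargement or weakening of the effect for a reason unrelated to cabozantinib. The analysis also discards deaths: in the scenarios below with NPACT, about 470 to 515 of the 621 remain.

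**Working it through.** **1. The plan's own figure.** Inputs from SAP 2.4: "90% power for a 2-sided log-rank test at 5% level of significance", HR 0.76, allocation "507 subjects in cabozantinib arm and 253 subjects in placebo arm", 621 deaths.

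- Schoenfeld events: (1.960 + 1.282)² / [(2/3)(1/3)(ln 0.76)²] = 10.51 / 0.01674 = 628, against 621 stated.
- Power at 621 deaths: Φ(√(621 × 2/9) × 0.2744 − 1.960) = Φ(1.264) = 89.7% for a fixed design, and 89.2% with the two interim looks.

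The design reproduces, so its inputs can be used for the check.

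**2. The mechanism by hand.** Assumptions not in the documents: half of each arm has death hazard h and half has 2h, identically in both arms, so OS is equal. Only the better-prognosis half starts NPACT, at 0.15 per month on placebo and 0.05 on cabozantinib. The median of 8.2 months (SAP 2.4) fixes h: with x = exp(−8.2h), x + x² = 1, so x = 0.618 and h = 0.0587.

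Among subjects alive and uncensored at month t, the better-prognosis share is f = exp(−(h+r)t) / [exp(−(h+r)t) + exp(−2ht)], where r is the NPACT rate. The hazard is h(2 − f), so the ratio is (2 − f for cabozantinib) / (2 − f for placebo).

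| t (months) | f placebo | f cabozantinib | hazard ratio |
|---|---|---|---|
| 3 | 0.432 | 0.507 | 0.952 |
| 6 | 0.366 | 0.513 | 0.910 |
| 12 | 0.251 | 0.526 | 0.843 |

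Without NPACT censoring, f is the same in both arms (0.587 at 6 months) and the ratio is 1.

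**3. Simulation of the same model.** 507 and 253 subjects, uniform entry over 760/31.5 = 24.1 months, cutoff at the 621st death, unstratified two-sided 5% log-rank (stratum proportions are not given), 3,000 to 4,000 trials per scenario. True OS is equal. The ITT analysis gave HR 1.00 and 4.4% to 5.9% two-sided rejection throughout. The nominal rate per side is 2.5%.

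| NPACT goes to | Placebo / cabozantinib use | Censored HR | Favours cabozantinib | Favours placebo |
|---|---|---|---|---|
| nobody | 0 / 0 | 1.00 | 2.8% | 2.6% |
| better prognosis, balanced | 30% / 30% | 1.00 | 2.7% | 2.4% |
| unrelated to prognosis | 40% / 24% | 1.00 | 2.7% | 2.2% |
| better, 1.5-fold hazard gap | 28% / 19% | 0.97 | 4.5% | 1.0% |
| better, 2-fold | 35% / 21% | 0.91 | 15% | 0.0% |
| better, 3-fold | 40% / 23% | 0.82 | 49% | 0.0% |
| worse, 2-fold | 28% / 14% | 1.07 | 0.5% | 10% |
| better, 2-fold, more on cabozantinib | 21% / 35% | 1.10 | 0.3% | 16.5% |

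Bias needs both conditions together: use related to prognosis and use that differs by arm.

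**4. Milder models.** With continuous prognosis and NPACT following progression (23% to 36% of placebo and 17% to 30% of cabozantinib subjects), the HR was 0.93 to 0.97 and 4.5% to 10.8% of trials falsely favoured cabozantinib. In a similar model with an illustrative prognostic stratum, about 32%/26% use gave HR 0.95 unstratified and 0.96 stratified. About 17%/14% gave 0.97 to 0.98, and 10%/8% gave 0.98.

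**5. Effective NPACT.** Let NPACT start independently of prognosis, halve the hazard, and be used by 48% of placebo and 21% of cabozantinib subjects, with a true HR of 0.80 without it. ITT then gives 0.97 and the censored analysis 0.80. Here censoring recovers its target.

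**The case against.** No decision rests on 7.1.4. The primary analysis counts every death, SAP 7.1.2 states its null for the primary endpoint, and SAP 7.3 makes this analysis exploratory. That stands: the rejection rates above describe how misleading the result could look, not an error rate of the trial.

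A reader might infer that the bias runs toward cabozantinib. The documents do not support that. They give no rate, timing or prognostic pattern for NPACT, and the table shows both directions and none. Protocol 1.4.2 says no second-line therapy is approved after sorafenib, so low use and a small bias are plausible. The only randomized PFS comparison in the protocol (1.3.3.3.2, 1.4 versus 2.5 months, measured from Week 12) was not statistically significant, so a large gap in time to progression cannot be taken from it.

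A reader might also infer that a benefit in the censored analysis with equal ITT OS must be an artefact. Step 5 shows that it need not be.

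The contrast with PFS has limits too. Counting NPACT as an event, as the PFS2 analysis does, would no longer measure OS. SAP 6.6 already summarizes NPACT by arm, which gives context but no correction.

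What remains is that 7.1.4 depends on an assumption it does not state, and the documents' own stopping rule makes that assumption doubtful.

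**Conclusion.** The point holds as a weakness in a supportive analysis. Plain censoring at NPACT is valid for a no-subsequent-therapy comparison only if starting NPACT is unrelated to prognosis given arm and strata. If fitter subjects receive it and placebo subjects receive it more or earlier, the HR under equal OS is typically about 0.91 to 0.98, and 0.82 in the most extreme scenario. It is about 1.07 to 1.10 in the two-fold scenarios where the pattern reverses, and 1.00 if use is balanced or unrelated to prognosis. NPACT rates, prognosis classes and their hazard gaps are assumptions.

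It would be wrong to read this as inflated Type I error or as a flaw in the primary test. It would also be wrong to call 7.1.4 the only other OS analysis: it is the only one that alters the censoring rules. The change is worth making because it is cheap and because a bias of unknown sign weakens a robustness check.

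**What to change.** In SAP 7.1.4:

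- State that censoring is at the start date of the systemic NPACT or liver-directed therapy, and that the target is the hypothetical effect had no subject received such therapy.
- Add a stratified Cox analysis with inverse-probability-of-censoring weights (IPCW). Model the start of therapy on arm, strata, radiographic progression, treatment discontinuation, and the latest ECOG status, Child-Pugh score, AFP, albumin and bilirubin. Use a robust or bootstrap confidence interval.
- Report it beside the plain-censored result and describe both as exploratory.

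The data are already planned: therapy dates in protocol 5.5.2, covariates in protocol Appendix A. The cost is one more model and a SAP revision before unblinding, which SAP 4.8 provides for.

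IPCW is a partial correction. It assumes no unmeasured confounding. ECOG, albumin and bilirubin have no scheduled collection after the 30-day visit. Child-Pugh and AFP stop at the later of 8 weeks after progression or the decision to discontinue, so late starts of therapy would rest on old values. In a small check (150 replicates, true HR 1), weighting moved the HR from 0.935 to 0.983 with prognosis fully observed. With a proxy of correlation 0.7 it moved from 0.953 to 0.974, under half of the bias: (0.974 − 0.953)/(1 − 0.953) = 45%. The standard deviation of the log HR rose from 0.094–0.100 to 0.098–0.118.

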# 7.2 Secondary Efficacy Endpoints

The secondary efficacy endpoints for this study are duration of PFS and ORR. Formal hypothesis tests are planned for the secondary efficacy endpoints.

# 7.2.1 Progression-Free Survival (PFS)

#### 7.2.1.1 Definition

Duration of PFS is defined as the time from randomization to the earlier of the date of radiographic progression or date of death due to any cause.

PFS (months) =(earliest date of progression, death, censoring – date of randomization + 1)/30.4375

The primary analysis of PFS will include all subjects in the ITT population and will include radiographic progression events as determined by the investigator per RECIST 1.1 and deaths.

The recorded date of radiographic progression is the date of the tumor assessment visit at which progression is declared. If multiple scan dates are associated with a tumor assessment visit, the earliest assessment date within the set will be chosen as the progression date.

Only adequate tumor assessments (ATAs) will be considered in the determination of radiographic progression and censoring dates. For the purpose of this study, ATA is defined as one that results in a time point assignment of: response (complete or partial), stable disease/(non-CR, non-PD), or progression. For PFS, ATA is based on soft tissue evaluation by CT/MRI and/or new lesions identified by bone scan.

General censoring rules for the primary analysis of PFS are described below:

• Subjects who receive systemic or liver directed local NPACT or non-protocol radiation therapy (other than to bone) or surgery to resect tumor lesions before experiencing an

event will be right censored at the date of the last ATA on or prior to the date of initiation of subsequent therapy/surgery. If there is no such tumor assessment after randomization, the subject will be right censored on the date of randomization.

- Subjects who have not experienced an event (and are not otherwise censored) at the time of data cutoff will be right censored on the date of their last tumor assessment after randomization that is on or prior to the data cutoff. If there is no such tumor assessment after randomization, the subject will be right censored on the date of randomization.
- Subjects who miss two or more ATAs (operationally defined as 126 days without an ATA) followed by an event (progression or death) will be right censored on the date of their most-recent ATA prior to the missing assessments. If there is no such tumor assessment after randomization, the subject will be right censored on the date of randomization

# 7.2.1.2 Hypothesis

The hypotheses to be evaluated in the analysis of the PFS are:

$$H_0$$
:  $S(t)_{cabozantinb} = S(t)_{placebo}$ 

$$H_A$$
:  $S(t)_{cabozantinb} \neq S(t)_{placebo}$ 

where  $S(t)_{Cabozantinib}$  and  $S(t)_{Placebo}$  are the survivor functions for PFS for the cabozantinib and placebo arms, respectively.

#### 7.2.1.3 Primary Analysis

The hypothesis testing of PFS between the two treatment arms will occur only if the result of either an interim analysis or the final analysis of OS achieves statistical significance. The primary analysis of PFS will include all subjects in the ITT population.

The summaries (median and 95% CI, stratified and unstratified log-rank p-values, stratified and unstratified HRs and their 95% CI) and graphs described in section 7.1.3 will be generated for PFS using a 2-sided level of significance,  $\alpha$ =0.04.

If the p-value for the stratified log-rank test for PFS is less than 0.04 and the HR is < 1, the null hypothesis will be rejected and it will be inferred that PFS is superior in the cabozantinib arm compared with the placebo arm.

### 7.2.1.4 Sensitivity Analyses

The primary analysis (PFS1) and 2 types of sensitivity analyses (PFS2 and PFS3) are outlined in Table 3. These analyses will include all subjects in the ITT population. Summaries and graphs as described in section 7.1.3 will be presented.

The sensitivity analyses (PFS2 and PFS3) define additional clinical outcomes as events and also evaluate the impact of informative censoring.

For PFS2 analysis, the following are considered as events:

- Radiographic progression per RECIST 1.1
- Death due to any reason
- Treatment discontinuation due to clinical deterioration
- Receipt of systemic non-protocol anti-cancer therapy (NPACT)
- Receipt of local liver-directed NPACT
- Radiation (other than to bone)
- Surgery to resect tumor lesions

For PFS3 analysis, the following are considered as events:

- Radiographic progression per RECIST 1.1
- Death due to any reason
- Treatment discontinuation due to clinical deterioration

Table 3: Event and censoring rules for primary and sensitivity analyses of PFS

Count as censored						
or event at earliest						
outcome criterion		DEG4		DEG.		DEG.
met	PFS1		PFS2		PFS3	
Purpose	Primary		Sensitivity			nsitivity
Situation	Outcome	Date	Outcome	Date	Outcome	Date
No post baseline	Censored	Date of	Censored	Date of	Censored	Date of
assessment		randomization		randomization		randomization
Radiographic PD	Event	Date of PD	Event	Date of PD	Event	Date of PD
Death	Event	Date of death	Event	Date of death	Event	Date of death
Subsequent	Censored	Date of last	Event	Date of NPACT	Censored	Date of last
systemic or local		ATA on or				ATA on or
liver directed non-		prior to				prior to
protocol anti-		NPACT				NPACT
cancer therapy						
(NPACT)						
Radiation (other	Censored	Date of last	Event	Date of	Censored	Date of last
than to bone)		ATA on or		radiation		ATA on or
		prior to				prior to
		Radiation				Radiation
Surgery to resect	Censored	Date of last	Event	Date of surgery	Censored	Date of last
tumor lesions		ATA on or				ATA on or
		prior surgery				prior surgery
Event after more	Censored	Date of last	Censored	Date of last	Censored	Date of last
than two missed		ATA prior to		ATA prior to the		ATA prior to
ATAs (>126 days)		the missing		missing visits		the missing
		visits				visits
Treatment	NA	NA	Event	Date of	Event	Date of
Discontinuation				determination		determination
due to Clinical						
deterioration						
No Event by last	Censored	Date of last	Censored	Date of last	Censored	Date of last
ATA		ATA		ATA		ATA

ATA: Adequate tumor assessment; PD=Progressive Disease; NA=Not Applicable

# 7.2.2 Objective Response Rate (ORR)

#### **7.2.2.1 Definition**

For each subject, best overall response (BOR) is defined as the best tumor assessment category as determined by the investigator per RECIST 1.1 that occurs prior to any of the censoring events defined for the primary analysis of PFS as described in section 7.2.1.1. Tumor assessment categories are ranked as: confirmed complete response (CR), confirmed partial response (PR), stable disease (SD), progressive disease (PD) and not evaluable (NE). To be classified as confirmed CR or confirmed PR, confirmation must have occurred on a subsequent visit that is  $\geq 28$  days after the response was first observed.

The ORR is defined as the proportion of subjects with a BOR of confirmed CR or confirmed PR.

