#### **6.1.2 Subsequent Dose Administration**

Subjects should fast (with the exception of water) for at least 2 hours after eating the evening meal before taking their dose of study drug. After the 2-hour fast and before going to bed, subjects are to take the tablets with a minimum of 8 oz (240 mL) water with no more food intake for at least 1 hour postdose. If the subject's schedule requires taking cabozantinib during the day, the subject should be instructed to follow the same fasting recommendations.

Subjects should be instructed to not make up vomited doses or missed doses and to maintain the planned dosing schedule. Subjects should not make up for missed doses if more than 12 hours

have elapsed after the time the subject would usually take study drug. In the event of missed doses, subjects should not take two doses to make up for the one the subject missed.

Dose reductions and interruptions due to tolerance issues are outlined in Section 6.5.1.

Subjects will receive blinded study drug as long as they continue to experience clinical benefit in the opinion of the investigator or until the earlier of unacceptable toxicity, the need for subsequent systemic anticancer therapy/liver-directed local anticancer therapy, or until any of the other reasons for treatment discontinuation described in Section 3.6.

Treatment may continue after disease progression per RECIST 1.1 has been determined by the investigator as long as the investigator believes that the subject is still receiving clinical benefit from study treatment and that the potential benefit of continuing study treatment outweighs potential risk.

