### **Evaluation of Overall Timepoint Response (TPR)**

Target Lesion TPR	Non-target lesion TPR	New lesion TPR	Overall TPR
CR	CR or NA	No	CR*
CR	Non-CR/non-PD	No	PR*
CR	UE	No	PR*
PR	Non-PD or NA or UE	No	PR*
SD	Non-PD or NA or UE	No	SD
UE	Non-PD	No	UE
PD	Any	No or Yes or UE	PD
Any	PD	No or Yes or UE	PD
Any	Any	Yes	PD
NA	CR	No	CR*
NA	Non-CR/Non-PD	No	Non-CR/non-PD
NA	UE	No	UE
Non-PD	Non-PD	UE	UE

CR, complete response; PR, partial response; SD, stable disease; PD, progressive disease, UE, unable to evaluate; NA, not applicable (no such lesions at screening); Any, CR, PR, SD, PD, NA, or UE.

The overall response at a given time point does not depend upon the overall response assigned at any prior time point.

\*Subjects with an overall response of CR or PR must have a repeat tumor assessment performed no less than 4 weeks after the criteria for response are first met. However, the presence or absence of confirmation is not considered when assigning a time point response.

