### 7.2.2.4 Supportive Analyses

To provide a more detailed understanding of anti-tumor activity, the maximum tumor reduction since baseline in target lesions will be derived for those subjects who have baseline and at least one post-baseline measure. The maximum percent tumor reduction from baseline in target lesions for each arm will be displayed graphically using waterfall

plots. For each subject, data from time points after the first date of any of the censoring events defined for the primary analysis of PFS as described in section 7.2.1.1. will be excluded from the waterfall plots.

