## 7.5.2 **Duration of Objective Response**

Duration of objective response is defined as the time from the first documentation of objective response by the investigator that is subsequently confirmed at a visit that is  $\geq 28$  days later to disease progression or death due to any cause.

Duration of response (months) = (earliest date of progressive disease or death due to any cause or censoring – date of first objective response + 1)/30.4375

Duration of objective response will be computed only among subjects who experience an objective response (confirmed CR or confirmed PR). Dates of progression and censoring will be determined as described for the secondary endpoint analysis of PFS (see section 7.2.1).

Duration of objective response will be analyzed using the same analysis method (Kaplan-Meier) as for the analysis on PFS (see Section 7.2.1.3).

The analyses for duration of response will be performed only if ORR >10%.

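### The SAP's best-overall-response rule stops at PFS censoring events but not at progression, so a partial response confirmed only after RECIST progression counts as a confirmed response in the ORR test

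*SAP*

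**What the plan says.** **Counting window.** SAP 7.2.2.1 takes the best investigator-assessed category that "occurs prior to any of the censoring events defined for the primary analysis of PFS as described in section 7.2.1.1". The categories rank confirmed CR, confirmed PR, SD, PD, not evaluable. For a confirmed CR or PR, "confirmation must have occurred on a subsequent visit that is" at least 28 days after the response was first seen. Nothing requires that progression has not come in between.

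**What the censoring events are.** SAP 7.2.1.1 lists three: non-protocol systemic or liver-directed therapy, non-bone radiation, or "surgery to resect tumor lesions before experiencing an" event; no event by data cutoff; and two or more missed adequate assessments (126 days) followed by an event. Progression is on the other side of the definition: "Duration of PFS is defined as the time from randomization to the earlier of the date of radiographic progression or date of death". Table 3 likewise classes radiographic PD as an event for the primary PFS analysis.

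**RECIST text.** Protocol Appendix G says: "The overall response at a given time point does not depend upon the overall response assigned at any prior time point". Its paragraph on best overall response leaves the derivation to the statistical analysis of the series of time-point responses and names no stop at PD.

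**Data after progression.** Protocol 6.1.2 says "Treatment may continue after disease progression per RECIST 1.1 has been determined by the investigator" if the investigator still sees clinical benefit. Scans continue to the later of 8 weeks after progression or the decision to stop treatment (SAP 2.1).

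**Use.** ORR is tested by two-sided Fisher exact test at 0.01 once OS is significant (SAP 7.2.2.3 and 7.3). Duration of response ends at the "earliest date of progressive disease or death due to any cause or censoring" (SAP 7.5.2), with progression dates taken from the PFS rules.

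**The concern.** Because PD is not a censoring event, it does not end the period in which a response or its confirmation may be collected. Because PD ranks below confirmed PR, an earlier PD does not override a later PR. A subject who progressed before any confirmation can therefore be classed as a confirmed responder.

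That a subject has both a response and a PFS event is not the problem; every responder who later progresses has both. The problem is the order. Here PD precedes confirmation, so the response had already ended under the PFS rules by the time it was confirmed. At stake is the classification of some subjects in a formally tested secondary endpoint. A programmer who follows the text counts them; one who assumes a customary stop at PD does not.

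**Working it through.** **Plan's own figure.** The documents give no expected ORR, no power for ORR and no rate of response after progression, so there is no figure to reproduce. The check compares the rules and applies them to an example.

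**Step 1: can PR, PD, PR occur under Appendix G?** PR is at least a 30% fall from the baseline sum. PD is at least a 20% rise, and at least 5 mm, from the lowest sum so far. The references differ, so both can be met in turn. Assumed sums, no new lesions, no non-target progression:

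| Visit | Sum (mm) | Change from baseline | Change from nadir | Response |
|---|---|---|---|---|
| Baseline | 100 | – | – | – |
| W9 | 65 | (65 − 100)/100 = −35% | new nadir | PR |
| W17 | 80 | −20% | (80 − 65)/65 = +23%, +15 mm | PD |
| W25 | 68 | (68 − 100)/100 = −32% | (68 − 65)/65 = +4.6% | PR |

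**Step 2: apply SAP 7.2.2.1.** W9 to W25 is 16 weeks, or 112 days, which exceeds 28. W25 is a subsequent visit. No non-protocol therapy is assumed, and every visit gave an adequate assessment, so no censoring event has occurred. Best overall response is confirmed PR. The PFS event is dated W17. The only post-progression scan needed is the one due 8 weeks after PD.

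**Step 3: compare with SAP 7.5.2.** Response starts at W9 and ends at PD at W17. On nominal dates the duration is (56 + 1)/30.4375 = 1.9 months, and it ends 8 weeks before the scan that confirms the response. The duration definition presupposes an order that the response definition does not enforce.

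**Step 4: sensitivity of the ORR test.** Inputs: 507 and 253 subjects (SAP 2.4; SAP 7.2.2.3 analyses all ITT subjects), with the placebo responder count assumed. With n responders in total, the probability that k are on placebo is C(253, k) × C(507, n − k) / C(760, n). The two-sided p sums all outcomes no more probable than the one observed.

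- 12 versus 0: 0.0074 for k = 0, plus 0.0036 for k = 9 to 12, gives p = 0.0110. Not significant at 0.01.
- 13 versus 0: 0.0049 for k = 0, plus 0.0015 for k = 10 to 13, gives p = 0.0064. Significant.
- With 1 placebo responder, the same calculation gives p = 0.0165 for 16 and p = 0.0099 for 17.

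One cabozantinib subject is 1/507 = 0.2 percentage points of ORR. The protocol (9.3.2) restricts this analysis to subjects with measurable disease; with smaller denominators the exact p-values would shift.

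**The case against.** **It is a slip in wording, and the intent is clear.** The duration-of-response definition runs from response to progression, and best response is to be assessed per RECIST 1.1. This makes it likely that a stop at PD was meant. But no sentence in either document says so, and the trial's own RECIST appendix contains no such stop. The Appendix G sentence on independence governs the assignment of time-point responses; it does not itself say that assessments after PD count towards best response. It does mean that a PR can be recorded after PD, and SAP 7.2.2.1 then counts it.

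**The route is narrow.** This stands. Under Appendix G any new lesion or unequivocal non-target progression makes the time point PD, and while it persists a later PR is blocked. What remains is mainly PD by target-lesion sum that then reverses; the example needs a fall of (80 − 68)/80 = 15% after PD.

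**The error rate is not affected.** A reader might infer that the ORR test's Type I error is inflated. The documents do not support that: the rule is prespecified and identical in both arms, treatment is double-blind, treatment past progression is open to both arms and the scan schedule is common. With no treatment effect, responses after PD are not expected to favour either arm.

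**The size is unknown.** A reader might also infer a material bias towards cabozantinib. Such cases need tumour shrinkage, so an excess there is plausible, but no document figure supports it or any rate. That one responder can flip a Fisher test at its boundary is true of any response rule; it shows sensitivity, not likelihood.

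**Duration and waterfall arguments.** If both the first PR and its confirmation follow PD, the duration formula ends before it starts. This is secondary: it needs at least two scans after PD, and duration is analysed only if ORR exceeds 10%, whereas 13/507 is 2.6%. The waterfall plot drops data only after "any of the censoring events defined for the primary analysis of PFS as described in section 7.2.1.1. will be excluded" from it, the same cut, but it is descriptive and carries no test.

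**Conclusion.** The point holds as a flaw in the response definition. As written, SAP 7.2.2.1 classes a PR that is confirmed only after RECIST progression as a confirmed response, and this conflicts with the order built into SAP 7.5.2. The classification follows from the text; the example shows that it is possible, not how often it happens.

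The effect is probably small. It could move the ORR estimate upward, and it could decide the ORR test only if the count sits at the boundary, for example 12 against 13 cabozantinib responders. That illustration rests on 507 and 253 subjects analysed and no placebo responders. The OS and PFS analyses are not touched. A correction before unblinding is worth making because the endpoint is formally tested and the change is simple.

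**What to change.** In SAP 7.2.2.1, define best overall response from assessments up to and including the first radiographic progression per RECIST 1.1, or before the first censoring event of the primary PFS analysis, whichever is earlier. Add that a confirmed CR or PR requires both the first response and its confirming scan to precede first progression.

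This also removes a related uncertainty. The therapy, radiation and surgery rule applies only before a PFS event, so for a subject who has already progressed it is arguable whether later therapy closes the window at all.

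Applying the same cut to the waterfall plot in 7.2.2.4 is optional. Shrinkage after progression can be shown in a listing.

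The cost is one or two sentences in a SAP revision before unblinding, which SAP 4.8 provides for. No data collection or clinical procedure changes. The observed ORR may be slightly lower.
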